7.2 ADVERSE EVENTS AND SERIOUS ADVERSE EVENTS

7.2.1 DEFINITION OF ADVERSE EVENTS (AE)

Adverse event means any untoward medical occurrence associated with the use of an intervention in humans, whether or not considered intervention-related (21 CFR 312.32 (a)).

7.2.2 DEFINITION OF SERIOUS ADVERSE EVENTS (SAE)

An adverse event (AE) is considered “serious” if, in the view of either the investigator or sponsor, it results in any of the following outcomes:

- Death
- A life-threatening adverse event (of note, the term “life-threatening” refers to an event in which the participant was at risk of death at the time of the event, rather than to an event which hypothetically might have caused death if it were more severe)
- inpatient hospitalization or prolongation of existing hospitalization
- a persistent or significant incapacity or substantial disruption of the ability to conduct normal life functions
- or a congenital anomaly/birth defect.

Important medical events that may not result in death, be life-threatening, or require hospitalization may be considered serious when, based upon appropriate medical judgment, they may jeopardize the participant and may require medical or surgical intervention to prevent one of the outcomes listed in this definition. Examples of such medical events include allergic bronchospasm requiring intensive treatment in an emergency room or at home, blood dyscrasias or convulsions that do not result in inpatient hospitalization, or the development of drug dependency or drug abuse.

7.2.3 CLASSIFICATION OF AN ADVERSE EVENT

7.2.3.1 SEVERITY OF EVENT

For adverse events (AEs), the following guidelines will be used to describe severity:

- **Mild** – Events require minimal or no treatment and do not interfere with the participant’s daily activities.
- **Moderate** – Events result in a low level of inconvenience or concern with the therapeutic measures. Moderate events may cause some interference with functioning.
- **Severe** – Events interrupt a participant’s usual daily activity and may require systemic drug therapy or other treatment. Severe events are usually potentially life-threatening or incapacitating. Of note, the term “severe” does not necessarily equate to “serious.”

7.2.3.2 RELATIONSHIP TO STUDY INTERVENTION

All adverse events (AEs) must have their relationship to study intervention assessed by the researchers who examine and evaluate the participant based on temporal relationship and his/her clinical judgment. The degree of certainty about causality will be graded using the categories below. In a clinical trial, the study product must always be suspect.

- **Related** – The AE is known to occur with the study intervention, there is a reasonable possibility that the study intervention caused the AE, or there is a temporal relationship between the study intervention and event. Reasonable possibility means that there is evidence to suggest a causal relationship between the study intervention and the AE.
- **Not Related** – There is not a reasonable possibility that the administration of the study intervention caused the event, there is no temporal relationship between the study intervention and event onset, or an alternate etiology has been established.

7.2.3.3 EXPECTEDNESS

The Principal Investigator will be responsible for determining whether an adverse event (AE) is expected or unexpected. An AE will be considered unexpected if the nature, severity, or frequency of the event is not consistent with the risk information previously described for the study intervention.

7.2.4 TIME PERIOD AND FREQUENCY FOR EVENT ASSESSMENT AND FOLLOW-UP

The occurrence of an adverse event (AE) or serious adverse event (SAE) may come to the attention of study personnel during study visits and interviews of a study participant, or upon review by a study monitor.

All AEs including local and systemic reactions not meeting the criteria for SAEs will be captured on the appropriate case report form (CRF). Information to be collected includes event description, time of onset, assessment of severity, relationship to study activities, and time of resolution/stabilization of the event. All AEs occurring while on study will be documented appropriately regardless of relationship. All AEs will be followed to adequate resolution.

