2.3 RISK/BENEFIT ASSESSMENT

2.3.1 KNOWN POTENTIAL RISKS

Physical risk includes (a) minor risk of discomfort or injury while installing a child restraint and (b) minor risk of discomfort from heat while installing a car seat in an outdoor setting during hot weather.

Psychological risks include (a) embarrassment from engaging in the research protocol, which involves physical movement in the back seat of a vehicle, and (b) embarrassment to answer questionnaires that are mildly invasive, such as household income.

There is minimal social risk from participating in this study. The primary risk results from the possibility for a breach of confidentiality. No data we collect will be highly personal, but we will collect information that participants may wish to keep private (such as household income), and the risk of a confidentiality breach is a social risk.

Participants will use their own smartphone to participate in the study and in some cases may incur small costs to use their phone. There are no known legal risks involved in study participation.

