5 STUDY INTERVENTION

5.1 STUDY INTERVENTION(S) ADMINISTRATION

5.1.1 STUDY INTERVENTION DESCRIPTION

All visits will be conducted by two individuals, a researcher (who is also certified as a CPS technician) and a technician. Following baseline activities, the researcher will inform the participant of their random assignment to a condition, either installation with a certified technician via interactive virtual presence or installation via the traditional live technician interaction. In cases where there is more than one restraint in the vehicle, the researcher will use a random number generator to select one of the restraints as the target for the research.

Those parents randomly assigned to the interactive virtual presence condition will be instructed how to connect to the interactive virtual presence program using their personal smartphone. Participants will connect to the interactive virtual presence program, view a brief online instructional video on using it, and then connect remotely to a certified technician.

Ensuring ecological validity and pragmatic trial practice, the researcher and local technician will purposely “stay away” through the remote installation process, allowing the parent and remote technician to engage via interactive virtual presence to install the restraint correctly in the vehicle. Remote technicians will guide the interaction following standard Safe Kids Worldwide practice for live in-person installations and participants will physically install and adjust the restraint into their own vehicle.

Those parents assigned to the control condition, installation by a live technician, will engage in standard procedures at Safe Kids Worldwide car seat checks to install the target restraint into the vehicle. The live technician will not be the same individual as the researcher, although they will both be present at the same location during the research protocol.

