8.3 STATISTICAL ANALYSES

Descriptive Statistics and Covariates. Descriptive statistics for participants randomized to each intervention will be summarized for each outcome using measures of central tendency (mean, median, proportion) and variability (variance, standard deviation, range). Several covariates may impact the relation between the intervention and the outcome measures of interest, and they will be similarly summarized descriptively. These include demographics (age, gender, target child birth order, race, ethnicity, SES); study site; type of vehicle; type of child restraint (including forward- vs. rear-facing); and attitudes, beliefs, and behaviors surrounding child restraints. Because parents will be randomized to the interventions, we expect covariates to be balanced across intervention groups. We will assess balance across intervention groups and utilize covariates in the primary analyses if appropriate. We also will estimate interaction effects to determine whether the intervention is more or less effective among particular subgroups that are adequately represented in the sample.

Primary Analyses. We have three specific aims. Specific Aim 1 is to identify how accurate parents are at installing child restraints using instructions from technicians via interactive virtual presence. We expect to find over 90% or greater of restraints are installed correctly in all respects. We also will investigate individual components of installation and expect over 90% of components, across participants, will be installed correctly. 95% confidence intervals for all of these outcomes will be calculated and presented graphically as a Forrest Plot with a reference line set at 0.90. Identical analyses will be conducted for the group randomized to in-person installation.

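### Adverse events are found only through unsolicited routes, and on-site staff keep away during installation in the remote arm only, so minor caregiver harm could be noticed less often there

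*Combined protocol and SAP*

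**What the plan says.** **How events are found.** Section 7.2.4 says that an event "may come to the attention of study personnel during study visits and interviews of a study participant". The only other route it gives is a monitor's review. It names no scheduled question, checklist or recall window.

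**What happens once an event is known.** The same section is thorough here: "All AEs occurring while on study will be documented appropriately regardless of relationship". A case report form takes the description, onset, severity, relationship and resolution. Section 7.2.5 sends serious events to the IRB and the sponsor.

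**Who is near the caregiver.** Section 5.1.1 says that in the remote arm "the researcher and local technician will purposely “stay away” through the remote installation process". During that time the caregiver works with the remote technician over the live link. In the control arm the live technician and the researcher are both at the same location, and no stay-away rule is stated.

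**Which harms are foreseen.** Section 2.3.1 lists "minor risk of discomfort or injury while installing a child restraint" and discomfort from heat when installing outdoors in hot weather.

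**What is analysed.** Section 8.1 lists two installation endpoints and a knowledge questionnaire. Section 8.3 opens with "Descriptive statistics for participants randomized to each intervention will be summarized for each outcome" and then sets out three aims: accuracy, non-inferiority, and learning and retention. It mentions no adverse-event summary, by arm or overall.

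**The concern.** Unsolicited reporting compares two arms fairly only if an event has a similar chance of coming to light in each. Here the design changes who is close to the caregiver during the session in which the foreseen physical harms arise, and it does so in one arm only. These harms are minor, which is the kind most easily missed unless someone asks.

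The synopsis (section 1.1) says the technology could supplement or replace in-person checks. A reader weighing replacement will want to know whether caregivers fared as well physically. If minor events come to light less often under remote help, the recorded counts could make the arms look more alike than they are. An event that nobody asked about cannot be recovered at analysis.

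Section 7.2.3.3 also makes the frequency of an event part of judging whether it is unexpected. Frequency is hard to judge from unsolicited reports that are not tabulated by arm.

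**Working it through.** **1. Number per arm.** Section 8.2 gives 664 per group, 10% attrition and a total of 1476. Check: 2 × 664 = 1328, and 1328 / 0.90 = 1475.6, rounded up to 1476, or 738 per arm. The stated power also reproduces. With SE = 0.10 × √(2/664) = 0.00549, power at equal means is Φ(0.025/0.00549 − 1.96) = 0.995. At a true difference of 0.01 it is Φ(0.015/0.00549 − 1.96) = 0.780. The sample size is sound for installation accuracy, but it says nothing about safety, for which no rate is given.

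**2. Routes to detection, side by side.**

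| Point in the visit | Remote arm | Control arm |
|---|---|---|
| During installation | Remote technician on a live link; on-site researcher and technician keep away (5.1.1) | Live technician and researcher at the same location (5.1.1) |
| Straight after installation | Restraint inspected (7.1) | Restraint inspected (7.1) |
| 4-month visit | Restraint inspected (7.1) | Restraint inspected (7.1) |
| Standard adverse-event question | None stated | None stated |

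The arms differ only in the first row. The later rows are the same in both arms, but the inspections score the restraint.

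**3. What unequal detection would do (illustration only).** The event and detection rates below are assumptions, not figures from the documents. Recorded events = n × true rate × detection.

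Take n = 738, true rates of 2% live and 3% remote (ratio 1.5), and 90% detection in the live arm.

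- Live: 738 × 0.02 × 0.90 = 13.3 recorded (1.8%).
- Remote: 738 × 0.03 × detection, as follows.

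| Remote detection | Recorded remote | Rate | Observed ratio |
|---|---|---|---|
| 90% | 19.9 | 2.7% | 1.50 |
| 75% | 16.6 | 2.2% | 1.25 |
| 50% | 11.1 | 1.5% | 0.83 |

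Observed ratio = true ratio × (remote detection / live detection). A true ratio of 1.5 is hidden when the detection ratio is 1/1.5 = 0.67, and reversed below that. With equal detection the ratio is not distorted.

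**4. What the trial could show with perfect capture.** At the same assumed 2% and 3%, the standard error of the risk difference is √(0.02 × 0.98/738 + 0.03 × 0.97/738) = 0.0081. The 95% half-width is 1.96 × 0.0081 = 1.6 percentage points, against a difference of 1 point. Power at two-sided 0.05 is Φ(0.01/0.0081 − 1.96), about 23%. A comparison by arm would therefore be descriptive.

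**The case against.** The strongest reply is that the remote caregiver is not unobserved. Section 2.2 describes the technology as simultaneous visual and spoken contact, so a caregiver who is hurt is already talking to a certified technician. Section 5.1.1 has remote technicians follow the practice used for in-person installations. Both arms are inspected as soon as the session ends, interviews are a named route to detection, and known events must be recorded. Section 6.1 stops training at any sign of an adverse effect. All of this stands. It is why the under-count is a possibility and not an expected result. It does not close the gap, because none of these steps puts the same question to every caregiver.

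A reader might go further and infer that excess injury under remote help would be under-counted or go unreported. The documents do not support that. Known events go on a form, and serious ones go to the IRB and the sponsor. What is missing is a planned summary by arm.

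A reader might also infer that remote caregivers do more of the physical work, since "participants will physically install and adjust the restraint into their own vehicle" is said of that arm. Section 5.1.1 does not say who does the physical work in the control arm, and the synopsis objective describes parents installing in both. Unequal exposure is not established.

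Two further points are fair. The illustration rests wholly on assumed rates, and it reverses direction only in the scenario of 50% against 90% detection. Section 10 says other aspects are in the IRB protocol, so a standard question may exist there. If it does, section 7.2.4 need only cite it.

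**Conclusion.** The point holds in a limited form. As written, the plan describes only unsolicited capture, and the stay-away rule applies to the remote arm alone. Minor caregiver injury or heat discomfort could therefore be noticed less often in that arm. The live link and the post-installation inspection lessen the risk without removing it.

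Neither the size nor the direction of any bias can be computed from the documents. The two-thirds threshold shows how much detection inequality would hide an assumed 1.5-fold excess; it is not an estimate of what will happen. It would be wrong to conclude that the harm data are biased in favour of remote help.

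No endpoint, margin, test or sample size is affected, and the foreseen physical risk is minor. The change is still worth making before data collection, because it is cheap and the information cannot be recovered later.

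**What to change.** 1. **Section 7.2.4.** Have the on-site researcher ask every participant in both arms the same fixed question at the end of the initial installation session, including sessions that were stopped. For example: *Did you have any pain, injury, heat discomfort or other problem while installing the seat today?* Record yes or no on the adverse-event form, with the details already collected there for any yes. Asking it again at the 4-month visit is optional, for consistency; the re-installation there is unassisted and carries no stay-away rule for one arm.

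2. **Section 8.3.** Add a descriptive table by randomised arm, among all who started the session, of participants with an installation injury or heat event, any adverse event, any related adverse event and any serious adverse event. Give risk differences with exact or score 95% confidence intervals. State that the comparison is not powered and that a similar count does not show equal safety.

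**Cost.** A short wording change, one question put by a researcher who already attends every visit, and one table. More minor events will be recorded in both arms, so the counts will not be comparable with those from studies that rely on unsolicited reports.

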7.2.5 ADVERSE AND SERIOUS ADVERSE EVENT REPORTING

All serious adverse events will be reported to the IRB according to regulatory requirements. The Principal Investigator will report to the sponsor any serious adverse event in a timely manner. All serious adverse events (SAEs) will be followed until satisfactory resolution.

7.3 UNANTICIPATED PROBLEMS

7.3.1 DEFINITION OF UNANTICIPATED PROBLEMS (UP)

The Office for Human Research Protections (OHRP) considers unanticipated problems involving risks to participants or others to include, in general, any incident, experience, or outcome that meets all of the following criteria:

- Unexpected in terms of nature, severity, or frequency given (a) the research procedures that are described in the protocol-related documents, such as the Institutional Review Board (IRB)-approved research protocol and informed consent document; and (b) the characteristics of the participant population being studied;
- Related or possibly related to participation in the research (“possibly related” means there is a reasonable possibility that the incident, experience, or outcome may have been caused by the procedures involved in the research); and
- Suggests that the research places participants or others at a greater risk of harm (including physical, psychological, economic, or social harm) than was previously known or recognized.

7.3.2 UNANTICIPATED PROBLEM REPORTING

The investigator will report unanticipated problems (UPs) to the reviewing Institutional Review Board (IRB). The UP report will include the following information:

- Protocol identifying information: protocol title and number, PI's name, and the IRB project number;
- A detailed description of the event, incident, experience, or outcome;
- An explanation of the basis for determining that the event, incident, experience, or outcome represents an UP;

- A description of any changes to the protocol or other corrective actions that have been taken or are proposed in response to the UP.

To satisfy the requirement for prompt reporting, UPs will be reported using the following timeline:

- UPs that are serious adverse events (SAEs) will be reported to the IRB within 10 working days of the investigator becoming aware of the event.
- Any other UP will be reported to the IRB within 10 working days of the investigator becoming aware of the problem.

8 STATISTICAL CONSIDERATIONS

8.1 STATISTICAL HYPOTHESES

- Primary Endpoint(s):

(a) total number of inspection points that are correctly installed, translated into a percentage to account for different points for different (e.g., rear-facing vs forward-facing; seat belt vs LATCH) installations, and
(b) dichotomous measure of whether the restraint was installed correctly vs. not correctly

- Secondary Efficacy Endpoint(s):

results from a brief knowledge questionnaire

8.2 SAMPLE SIZE DETERMINATION

To conclude non-inferiority of the interactive remote presence condition with $\geq 80\%$ power, Type I error rate of .025, a non-inferiority margin of 0.025, and assuming a common SD of 0.10 (similar to that observed previously), we propose a sample size of 1476. This estimate conservatively assumes 10% attrition based on a two-sample test of non-inferiority difference in means.

The table below presents statistical power to declare non-inferiority between two means, as defined by the alternative hypothesis, assuming a common standard deviation of 0.10, a Type I error rate of 0.025, a sample size per group of 664, the non-inferiority margin (Δ) specified in the row, and the different combinations of intervention means (μ_1, μ_2) specified by the columns. As long as the difference between the two means is less than the assumed non-inferiority margin, the definition of non-inferiority is met and power can be calculated. However, as can be seen by each row of the table, as the difference in intervention means grows, statistical power will decrease.

To illustrate interpretation of the table, if the mean installation accuracy of in-person instruction is 0.90 and the mean installation accuracy of remote instruction is 0.90 (i.e., the two groups achieve equal accuracy), then 664 persons randomized to each group provides 99.5% power to declare non-inferiority of remote instruction to in-person instruction using a Type I error rate of .025, a non-inferiority margin of 0.025, and a common standard deviation of 0.10. Similarly, if the mean installation accuracy of in-person instruction is 0.90 and the mean installation accuracy of remote instruction is 0.89, the two means are not equal but the difference in means ($0.90 - 0.89 = 0.01$) remains less than the declared non-inferiority margin (0.025). Under this scenario, 664 persons randomized to each group provides 78% power to declare non-

inferiority of remote instruction to in-person instruction using a Type I error rate of .025, a non-inferiority margin of 0.025, and a common standard deviation of 0.10.

Table. Statistical Power assuming 664 persons randomized per group (total N = 1476 with conservatively-estimated 10% attrition).

		Combination of mean accuracy scores for intervention groups				
Δ	$\mu_1 = 0.90$ $\mu_2 = 0.90$	$\mu_1 = 0.90$ $\mu_2 = 0.8975$	$\mu_1 = 0.90$ $\mu_2 = 0.895$	$\mu_1 = 0.90$ $\mu_2 = 0.8925$	$\mu_1 = 0.90$ $\mu_2 = 0.8900$	
0.020	0.954	0.890	0.780	0.625	0.445	
0.025	0.995	0.984	0.954	0.890	0.780	
0.030	0.999	0.999	0.995	0.984	0.954	

8.3 STATISTICAL ANALYSES

Descriptive Statistics and Covariates. Descriptive statistics for participants randomized to each intervention will be summarized for each outcome using measures of central tendency (mean, median, proportion) and variability (variance, standard deviation, range). Several covariates may impact the relation between the intervention and the outcome measures of interest, and they will be similarly summarized descriptively. These include demographics (age, gender, target child birth order, race, ethnicity, SES); study site; type of vehicle; type of child restraint (including forward- vs. rear-facing); and attitudes, beliefs, and behaviors surrounding child restraints. Because parents will be randomized to the interventions, we expect covariates to be balanced across intervention groups. We will assess balance across intervention groups and utilize covariates in the primary analyses if appropriate. We also will estimate interaction effects to determine whether the intervention is more or less effective among particular subgroups that are adequately represented in the sample.

Primary Analyses. We have three specific aims. Specific Aim 1 is to identify how accurate parents are at installing child restraints using instructions from technicians via interactive virtual presence. We expect to find over 90% or greater of restraints are installed correctly in all respects. We also will investigate individual components of installation and expect over 90% of components, across participants, will be installed correctly. 95% confidence intervals for all of these outcomes will be calculated and presented graphically as a Forrest Plot with a reference line set at 0.90. Identical analyses will be conducted for the group randomized to in-person installation.

Specific Aim 2 will test whether child restraint installation by interactive virtual presence achieves installation accuracy at a rate not inferior to installation with a live technician. Two models will be computed, one with a measure of installation accuracy (proportion of all child restraint installation components performed correctly) as the dependent variable and the other with the dichotomous outcome of correct (100% correct installation across all components) vs. incorrect installation (<100% correct installation) as the dependent variable. Assuming that improvement is reflected by a positive value (that is, a higher post-training value is better), our primary model, based upon installation accuracy, is:

$$H_0: \Delta_{LIVE} - \Delta_{IVP} \geq \delta \text{ vs. } H_A: \Delta_{LIVE} - \Delta_{IVP} < \delta$$

where δ is the non-inferiority margin and IVP stands for interactive virtual presence. We will assume a non-inferiority margin of 0.025 for the primary analysis (see power analysis) and perform Analysis of

Covariance (ANCOVA) to determine if the difference of mean installation accuracy scores between the two groups falls below the non-inferiority margin of 0.025, after adjustment for the baseline measure of installation accuracy and other relevant covariates. Based on previous work, we do not anticipate non-normality of the continuous outcome variable of installation accuracy. However, we will assess normality using graphical techniques (normal probability plot, histograms) prior to analysis and will transform outcomes if appropriate. The one-sided non-inferiority test will be conducted using a Type I error of 0.025.

Specific Aim 3 will test parent learning and retention, both through measures of installation accuracy (after the intervention, at start of follow-up visit, and after parent re-installation during follow-up visit) and through the brief knowledge questionnaire administered at post and at follow-up. Six models will be computed using strategies identical to those for Aim 2 and predicting the following dependent variables: (a) installation accuracy (proportion of restraint components performed correctly at start of 4-month follow-up visit); (b) dichotomous outcome of correct vs incorrect installation at start of follow-up visit; (c) installation accuracy after parental re-installation during follow-up visit; (d) dichotomous outcome of correct vs incorrect installation after parental re-installation during follow-up visit; (e) knowledge questionnaire during post visit; and (f) knowledge questionnaire during follow-up visit.

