5.2 MEASURES TO MINIMIZE BIAS: RANDOMIZATION

Randomization lists will be generated by the study biostatistician and stored electronically. A separate randomization list will be generated for each site and all will utilize a randomly permuted block design to allow for balance among intervention arms as the research study progresses and to limit the ability of any research staff member from definitively knowing/predicting future assignment. Block sizes will range over all even numbers from 8 to 16 inclusive.

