7 STUDY ASSESSMENTS AND PROCEDURES

7.1 STUDY ASSESSMENTS

We will consider two primary outcomes, both derived from inspections of child restraint installations using objective coding sheets: (a) total number of inspection points that are correctly installed, translated into a percentage to account for different points for different (e.g., rear-facing vs forward-facing; seat belt vs LATCH) installations, and (b) dichotomous measure of whether the restraint was installed correctly vs. not correctly. Examples of inspection points include whether tether straps are twisted, whether the seat moves more than 1 inch to the left/right, whether seat belts are routed through the correct belt pathway, and whether the carrying handle is in the correct position.

Both outcomes will be collected at four time points: at baseline prior to any intervention, at post, immediately following the initial installation in both groups, at the start of the follow-up visit following 4 months of no active intervention by the research team, and at follow-up after parent installation without technician assistance.

We also will consider results from a brief knowledge questionnaire, which was adopted from an existing instrument. Secondary and covariate measures considered will include demographic traits of the participant (e.g., gender, race, ethnicity, SES, research site) and restraint (e.g., forward vs rear facing, LATCH vs seat belt installation), attitudes and beliefs about child restraints, perceived efficacy of the interventions, and reported behaviors using restraints.

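### Randomisation is stratified by site, but the primary ANCOVA does not commit to site; fixing it in advance is a small, free gain in precision

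*Combined protocol and SAP*

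**What the plan says.** Section 5.2 stratifies by site: "A separate randomization list will be generated for each site". The lists use permuted blocks, and "Block sizes will range over all even numbers from 8 to 16 inclusive". Section 4.1 names seven centres.

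For the primary Aim 2 model, section 8.3 compares mean accuracy between arms "after adjustment for the baseline measure of installation accuracy and other relevant covariates". Baseline accuracy is the only covariate named in that commitment.

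The covariate paragraph of section 8.3 lists candidates, among them "study site; type of vehicle; type of child restraint (including forward- vs. rear-facing". Section 7.1 also names research site among the covariate measures. Section 8.3 then says "Because parents will be randomized to the interventions, we expect covariates to be balanced across intervention groups", and continues: "We will assess balance across intervention groups and utilize covariates in the primary analyses if appropriate". It gives no criterion for what makes a covariate relevant or appropriate.

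The six Aim 3 models follow the Aim 2 strategy, so they inherit the same open choice.

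**The concern.** The plan restricts randomisation by site but leaves open whether the analysis will reflect that restriction. When a stratification factor predicts the outcome, stratifying makes the treatment estimate more precise. A model without the factor does not see that gain, so its standard error is too large.

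The only check the plan describes cannot settle the choice. Arm balance by site is guaranteed by the blocks, so a balanced table is no evidence that site can be left out. Two analysts following section 8.3 faithfully could fit different primary models and report different confidence limits against the 0.025 margin.

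What is at stake is precision already provided by the design, and one modelling decision that could otherwise be taken after data are seen.

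**Working it through.** **Inputs from the plan (sections 8.2 and 8.3).** Margin 0.025, SD 0.10, one-sided error 0.025 (z = 1.96), 664 per arm after 10% attrition, total 1476.

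**Assumptions (the documents give no figure).** R² is the share of variance left after baseline adjustment that site explains: 2%, 5%, 10% or 20%. ρ is the baseline-outcome correlation: 0.3 or 0.5 where used. Site effects are similar in both arms.

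**Step 1: reproduce the plan.** SE = 0.10 × √(2/664) = 0.005488.
- Equal means: Φ(0.025/0.005488 − 1.96) = Φ(2.595) = 0.995, as stated.
- Deficit 0.01: Φ(0.015/0.005488 − 1.96) = Φ(0.773) = 0.780, as stated.
- 664/0.9 = 738 per arm after rounding up, and 2 × 738 = 1476, as stated.

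**Step 2: can a balance check inform site?** An incomplete block of 16 can leave an arm difference of at most 8 at a site at randomisation. The scheme was simulated 20,000 times with seven near-equal sites and 20,000 times with assumed unequal sites (500, 400, 250, 150, 100, 50, 26). The largest arm difference at one site was 7 and 8. The smallest p from a chi-square test of site by arm was 0.9993 and 0.934. Site would not be flagged.

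**Step 3: error with site omitted.** The model uses SE, while the true SD of the estimate is SE × √(1 − R²). One-sided error = 1 − Φ(1.96/√(1 − R²)):

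| R² | 2% | 5% | 10% | 20% |
|---|---|---|---|---|
| Error | 0.0239 | 0.0222 | 0.0194 | 0.0142 |

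**Step 4: power at true deficit d.** SE = 0.10 × √(1 − ρ²) × √(2/n).
- Site omitted: Φ((0.025 − d − 1.96 × SE)/(SE × √(1 − R²))).
- Site included: Φ((0.025 − d)/(SE × √(1 − R²)) − 1.96).

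Example: n = 664, ρ = 0, R² = 10%, d = 0.01. SE × √0.9 = 0.005207. Omitted: Φ((0.015 − 0.010757)/0.005207) = Φ(0.815) = 79.2%. Included: Φ(2.881 − 1.96) = Φ(0.921) = 82.2%.

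The 664 rows take 0.10 as the SD after baseline adjustment. The 738 rows assume no attrition, because section 7.1 takes this measure "at post, immediately following the initial installation in both groups".

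Power at d = 0.01, omitted / included (%):

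| Case | R² 2% | 5% | 10% | 20% |
|---|---|---|---|---|
| n = 664, ρ = 0 | 78.3 / 78.8 | 78.6 / 80.1 | 79.2 / 82.2 | 80.6 / 86.3 |
| n = 738, ρ = 0.3 | 85.8 / 86.2 | 86.2 / 87.3 | 86.8 / 89.0 | 88.2 / 92.2 |
| n = 738, ρ = 0.5 | 91.6 / 91.9 | 92.0 / 92.7 | 92.5 / 93.9 | 93.7 / 96.1 |

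Before rounding, the gains for R² of 2%, 5%, 10% and 20% are 0.6, 1.5, 2.9 and 5.7 points (first row); 0.4, 1.1, 2.1 and 4.0 (second); 0.3, 0.7, 1.4 and 2.4 (third).

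**Step 5: smaller deficits.** At d = 0.005 the largest gain is in the case n = 664, ρ = 0, R² = 20%. With SE × √0.8 = 0.004909, power omitted is Φ(0.009243/0.004909) = Φ(1.883) = 97.0%, and included is Φ(4.074 − 1.96) = Φ(2.114) = 98.3%, a gain of about 1.3 points. At d = 0 the gain is at most 0.1 point.

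**Step 6: simulated ANCOVA.** With N = 1476, ρ = 0.3, seven near-equal sites and blocks of 8 to 16 (6,000 trials per cell), power at d = 0.01 omitted / included was 0.855 / 0.860, 0.860 / 0.872, 0.867 / 0.890 and 0.885 / 0.922 for the four R² values. Simulated error (12,000 trials, Monte Carlo SE 0.0014) was 0.0228 omitted and 0.0257 included at R² = 5%, and 0.0143 and 0.0258 at 20%. This agrees with the formulas.

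**The case against.** The strongest reply is that no conclusion is at risk: leaving site out errs on the safe side. That stands, and it limits the point to an improvement.

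Second, the larger gains need generous inputs. The 5.7 points require a 20% site share and 664 per arm. Section 8.2 builds 664 on attrition ("This estimate conservatively assumes 10% attrition based on a two-sample test of non-inferiority difference in means"), yet the Aim 2 measure is taken at the same visit as the installation. At SD 0.10, a 20% share means a between-site SD of √0.20 × 0.10 = 0.045, nearly twice the margin, and nothing in the documents supports that. With 738 per arm and a 2% to 5% share, the gain is 0.3 to 1.1 points. This also stands.

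Third, site effects may not be similar in both arms. Section 5.1.1 distinguishes local from remote technicians and does not tie remote technicians to a site. If site differences arose only in the live arm, the pooled site effect would explain about a quarter of the assumed share, and the gain would shrink accordingly. Differences due to coders or populations would remain.

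Fourth, a reader might infer that the plan excludes site, or makes balance the sole test for a covariate. The documents support neither. The Aim 2 wording leaves room for site, sections 7.1 and 8.3 both name it as a candidate, and no significance test of balance is specified. What remains is that site is not committed to, and that the one check described is uninformative for it.

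Finally, the open list of other covariates leaves more analytic freedom than site does, because adding a balanced factor barely moves the estimate. That is a fair but separate point.

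**Conclusion.** The point holds as a free improvement. The plan stratifies by site without committing the primary model to site, and the balance check cannot decide the matter.

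For an assumed site share of 2% to 10%, omission lowers one-sided error to about 0.024 to 0.019 and forgoes about 0.3 to 2.9 points of power at a deficit of 0.01. The forgone power reaches 5.7 points only at a 20% share with 664 per arm. It is at most about 1.3 points at a deficit of 0.005 and essentially nil at equal means. All of this rests on assumed site shares and on similar site effects in both arms.

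A reader might infer that the trial risks a false claim of non-inferiority or is underpowered because of this gap. Neither follows. Error falls below 0.025, and power with site omitted is at least 78.3% at a deficit of 0.01 in every case examined, against the stated 78%.

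The calculations cover the continuous ANCOVA only and do not carry over to the dichotomous models.

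**What to change.** In the Aim 2 text of section 8.3, state that the primary ANCOVA contains arm, baseline installation accuracy and site as a seven-level fixed effect, whatever the balance table shows. Carry the site term to the continuous Aim 3 models (a, c, e and f).

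For the dichotomous models (Aim 2, and Aim 3 b and d), account for site by a method that keeps the chosen effect measure and tolerates small sites, for example a site-stratified Mantel-Haenszel risk difference. Simply adding seven levels to a logistic model, if that is what is intended, would make the odds ratio conditional on site and could cause separation. At the 90% fully correct rate expected in section 8.3, an assumed site of 26 participants has a 0.9^26 = 6% chance of no incorrect installation.

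The cost is a few sentences in section 8.3. Site is already recorded because randomisation uses it. In the ANCOVA the term takes six degrees of freedom out of roughly 1,328 (2 × 664) to 1,476 participants. Sample size, visits and data collection do not change.
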